4.2.1 For Dose Escalation Only

To be eligible for enrollment in dose escalation, a subject must meet ALL of the following criteria in addition to the inclusion criteria listed above for all subjects:

1. Has **evaluable** disease as defined as lesions that can be accurately measured at least in one dimension by radiographic examination or physical examination or other lesions such

as bone lesions, leptomeningeal disease, ascites, pleural/pericardial effusions, lymphangitis cutis/pulmonitis or hepatosplenomegaly from disease.

2. Has one of the following histologically confirmed tumors:

- Rhabdoid tumor:
 - Atypical teratoid rhabdoid tumor (ATRT) (Closed to enrollment)
 - Malignant rhabdoid tumor (MRT)
 - Rhabdoid tumor of the kidney (RTK)
 - Selected tumors with rhabdoid features
- INI1-negative tumor:
 - Epithelioid sarcoma (ES)
 - Epithelioid malignant peripheral nerve sheath tumor (EMPNST)
 - Extraskelatal myxoid chondrosarcoma (EMC)
 - Myoepithelial carcinoma
 - Renal medullary carcinoma (RMC)
 - Other INI1-negative malignant tumors (e.g., de-differentiated chordoma)

NOTE: Requires prior Sponsor approval

- Synovial sarcoma with SS18-SSX rearrangement (closed to enrollment)

NOTE: Evidence of diagnostic pathology of original biopsy confirmed by a CLIA/College of American Pathologists (CAP) other Sponsor-approved certified laboratory must be available.

3. **For subjects with ATRT, MRT, RTK, or tumors with rhabdoid features only:** The following test results must be available:

- Morphology and immunophenotypic panel consistent with rhabdoid tumor, and
- Loss of INI1 or SMARCA4 confirmed by IHC, or
- Molecular confirmation of tumor bi-allelic INI1 or SMARCA4 loss or mutation when INI1 or SMARCA4 IHC is equivocal or unavailable

4. **For subjects with INI1-negative tumor only:** The following test results must be available:

- Morphology and immunophenotypic panel consistent with INI1-negative tumors, and
- Loss of INI1 confirmed by IHC, or
- Molecular confirmation of tumor bi-allelic INI1 loss or mutation when INI1 IHC is equivocal or unavailable

5. **For subjects with synovial sarcoma only:** The following test results must be available:

- Morphology consistent with synovial sarcoma, and
- Cytogenetics or FISH and/or molecular confirmation (e.g., DNA sequencing) of SS18 rearrangement t(X;18)(p11;q11)

4.2.2 For Dose Expansion Only

To be eligible for enrollment in the Dose Expansion part, a subject must meet ALL of the following criteria in addition to the inclusion criteria for all subjects listed above:

1. Has **measurable** disease as defined in Section 8.5.3
2. Has one of the following histologically confirmed tumors:
 - Cohort 1 (closed to enrollment):
 - Atypical teratoid rhabdoid tumor (ATRT)
 - Cohort 2:
 - Malignant rhabdoid tumor (MRT)
 - Rhabdoid tumor of the kidney (RTK)
 - Selected tumors with rhabdoid features
 - Cohort 3 (INI1-negative tumors):
 - Epithelioid sarcoma (ES)
 - Epithelioid malignant peripheral nerve sheath tumor (EMPNST)
 - Extraskelatal myxoid chondrosarcoma (EMC)
 - Myoepithelial carcinoma
 - Renal medullary carcinoma (RMC)
 - Chordoma (poorly differentiated or de-differentiated)
 - Other INI1-negative malignant tumors **NOTE:** Requires prior Sponsor approval
 - Cohort 4 (closed to enrollment):
 - One of the tumor types defined in Cohorts 1 through 3 or synovial sarcoma with SS18-SSX rearrangement

NOTE: Evidence of diagnostic pathology of original biopsy confirmed by a CLIA/CAP other Sponsor-approved certified laboratory must be available.

3. For subjects with ATRT/MRT/RTK only - have the following test results available:
 - Morphology and immunophenotypic panel consistent with rhabdoid tumor, and
 - Loss of INI1 or SMARCA4 confirmed by IHC, or
 - Molecular confirmation of tumor bi-allelic INI1 or SMARCA4 loss or mutation when INI1 or SMARCA4 IHC is equivocal or unavailable

4. For subjects with INI1-negative tumors only – have the following test results available:
 - Morphology and immunophenotypic panel consistent with INI1-negative tumors, and
 - Loss of INI1 confirmed by IHC, or
 - Molecular confirmation of tumor bi-allelic INI1 loss/mutation when INI1 IHC is equivocal or unavailable
5. For subjects with synovial sarcoma with SS18-SSX rearrangement (in Cohort 4 only; Cohort 4 is closed to enrollment) - have the following test results available:
 - Morphology consistent with synovial sarcoma, and
 - Cytogenetics or FISH and/or molecular confirmation (e.g., DNA sequencing) of SS18 rearrangement t(X;18)(p11;q11)
6. **For subjects to be enrolled in Cohort 4 (Cohort 4 is closed to enrollment):** Able to swallow and retain orally administered tablets.

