 - Cohort 1 (**enrollment closed**):
 - Atypical teratoid rhabdoid tumor (ATRT)
 - Cohort 2:
 - Malignant rhabdoid tumor (MRT)
 - Rhabdoid tumor of the kidney (RTK)
 - Selected tumors with rhabdoid features
 - Cohort 3 (INI1-negative tumors):
 - Epithelioid sarcoma (ES)
 - Epithelioid malignant peripheral nerve sheath tumor
 - Extraskelatal myxoid chondrosarcoma (EMC)
 - Myoepithelial carcinoma
 - Renal medullary carcinoma
 - Chordoma (poorly differentiated or de-differentiated)
 - Other INI1-negative malignant tumors NOTE: Requires prior Sponsor approval
 - Cohort 4 (**enrollment closed**):
 - One of the tumor types defined in Cohorts 1 through 3 or synovial sarcoma with SS18-SSX rearrangement

NOTE: Evidence of diagnostic pathology of original biopsy confirmed by a CLIA/CAP or other Sponsor-approved certified laboratory must be available.

3. For subjects with ATRT/MRT/RTK only – have the following test results available:
 - Morphology and immunophenotypic panel consistent with rhabdoid tumor, and
 - Loss of INI1 or SMARCA4 confirmed by IHC, or
 - Molecular confirmation of tumor bi-allelic INI1 or SMARCA4 loss or mutation when INI1 or SMARCA4 IHC is equivocal or unavailable
4. For subjects with INI1-negative tumors only – have the following test results available:
 - Morphology and immunophenotypic panel consistent with INI1-negative tumors, and
 - Loss of INI1 confirmed by IHC, or
 - Molecular confirmation of tumor bi-allelic INI1 loss/mutation when INI1 IHC is equivocal or unavailable
5. For subjects with synovial sarcoma with SS18-SSX rearrangement (in Cohort 4 only. **Cohort 4 is closed to enrollment**) - have the following test results available:
 - Morphology consistent with synovial sarcoma, and
 - Cytogenetics or FISH and/or molecular confirmation (e.g., deoxyribonucleic acid [DNA] sequencing) of SS18 rearrangement t(X;18)(p11;q11)
6. **For subjects to be enrolled in Cohort 4 (Cohort 4 is closed to enrollment):**
Able to swallow and retain orally administered tablets

Exclusion Criteria:

Subjects meeting ANY of the following criteria must NOT be enrolled in this study:

1. Has had prior exposure to tazemetostat or other inhibitor(s) of enhancer of zeste homolog-2 (EZH2)
2. Is being actively treated for another concurrent malignancy or is less than 5 years from completion of treatment for another malignancy

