3 STUDY DESIGN

3.1 Overall Experimental Plan

This is a Phase 1, multicenter, open-label, dose escalation and expansion study of tazemetostat in pediatric subjects with select relapsed or refractory INI1- or SMARCA4-negative tumors. Subjects will be screened for eligibility within 14 days of the planned first dose of tazemetostat. A treatment cycle will be 28 days. Treatment with tazemetostat will continue until disease progression, unacceptable toxicity, or withdrawal of consent. Subjects will receive tazemetostat for a cumulative maximum of 2 years.

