15. Has sufficient tumor tissue (slides or blocks) available for central confirmatory testing of immunohistochemistry (IHC) and/or cytogenetics/FISH and/or DNA mutation analysis (required for study entry but enrollment based on local results).
16. Is willing and able to comply with all aspects of the protocol as judged by Investigator.
17. **For female subjects of childbearing potential:** Subject must:
 - Have a negative beta-human chorionic gonadotropin (β -hCG) pregnancy test at time of Screening and within 72 hours prior to planned first dose of tazemetostat (urine or serum test is acceptable however, positive urine tests must be confirmed with serum testing), and
 - Agree to use effective non-hormonal contraception, as defined in Section 8.5.11 from start of Screening until 6 months following the last dose of study treatment and have a male partner who uses a condom, or
 - Practice true abstinence (when this is in line with the preferred and usual lifestyle of the subject, see Section 8.5.11), or
 - Have a male partner who is vasectomized with confirmed azoospermia.
18. **For male subjects with a female partner of childbearing potential:** Subject must:
 - Be vasectomized or
 - Agree to use condoms as defined in Section 8.5.11 from the first dose of tazemetostat until 3 months following the last dose of tazemetostat, or
 - Have a female partner who is NOT of childbearing potential
19. **For subjects enrolling at sites in France only:** Is either affiliated with or a beneficiary of a social security category

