8.5.8 Tumor Sampling

8.5.8.1 Archive Tumor or Biopsy at Screening

An archival tumor block or biopsy, is required at Screening from all subjects enrolled in the study. As available the diagnostic pathology block or tumor tissue obtained at the time of the

subject's initial diagnosis and/or at the time of subsequent procedures will be acceptable. The Sponsor or its designee will return all blocks to the originating site on completion of the associated analyses. If a tumor block is not available, 10-20 unstained paraffin-embedded tumor tissue containing slides may instead be provided.

Study entry and eligibility will be based upon local diagnostic criteria. Independent central confirmation will not be required for study entry.

If archive tumor material is not available, tumor biopsy obtained during Screening is also acceptable. Adequate tissue must be available to prepare or provide 10-20 unstained paraffin-embedded tumor tissue slides.

Independent central confirmation will **not** be required for study entry. Central confirmation of diagnosis with appropriate IHC, karyotyping, and DNA sequencing as appropriate will be performed. CCI

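### The dose-expansion biomarker criterion omits tumors with rhabdoid features, so Cohort 2 can admit subjects without evidence of INI1 or SMARCA4 loss, which could dilute its ORR

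*Protocol*

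**What the plan says.** Section 4.2.2, criterion 2, lists three tumor types for Cohort 2: MRT, RTK and, as a separate entry, "Selected tumors with rhabdoid features". Cohorts 1 and 4 are marked closed to enrollment; Cohort 2 is not.

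The laboratory evidence needed for dose expansion is set out in the next three criteria:

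- Criterion 3 requires consistent morphology plus INI1 or SMARCA4 loss, by IHC or, where IHC is equivocal or unavailable, by molecular testing. Its heading is "For subjects with ATRT/MRT/RTK only - have the following test results available".
- Criterion 4 is headed "For subjects with INI1-negative tumors only – have the following test results available" and serves Cohort 3.
- Criterion 5 concerns synovial sarcoma in Cohort 4.

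The synopsis carries the same restriction as criterion 3: "For subjects with ATRT/MRT/RTK only – have the following test results available". For dose escalation, Section 4.2.1 makes the same demand of a wider group: "For subjects with ATRT, MRT, RTK, or tumors with rhabdoid features only". The synopsis text for escalation agrees with it.

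Section 3.1 describes the study as one in "pediatric subjects with select relapsed or refractory INI1- or SMARCA4-negative tumors", and SAP Section 3.1 describes the same population. On tissue, inclusion criterion 15 in Section 4.2 asks for material for central testing that is "required for study entry but enrollment based on local results". Section 8.5.8.1 adds: "Independent central confirmation will not be required for study entry".

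**The concern.** The stricter rule sits in the part of the study that tests no hypothesis (Section 14.1.1). The looser one sits in the part that carries the ORR test (Sections 14.1.2 and 14.2.1). A site applying Section 4.2.2 as written could enroll into Cohort 2 a tumor with rhabdoid morphology in which INI1 and SMARCA4 are intact or untested.

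The rationale in Section 1 ties EZH2 dependency to loss of these proteins, so a lower response rate would be expected without that loss. Such subjects would remain in the denominator, because Section 14.4.1 counts everyone who received a dose. If Cohort 2 then missed 3 responses in 20, the result could reflect who was enrolled as well as how active the drug is. The planned analyses could not separate the two: the only ORR subgroup in the SAP is prior radiotherapy (SAP Sections 3.2, 6.1 and 15.1). The benefit-risk summary in Section 1.6.6 is also written for INI1-negative tumors and does not speak to tumors without the loss.

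**Working it through.** **Step 1: does any other provision close the gap?**

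| Provision | Effect on a rhabdoid-features tumor in expansion |
|---|---|
| 4.2, criterion 7 | Local diagnostic pathology must be documented; no INI1 or SMARCA4 result is required |
| 4.2, criterion 15 | Tissue must be available; no result is needed before entry |
| 4.2.2, criterion 3 | Names ATRT, MRT and RTK; does not name this category |
| 4.2.2, criteria 4 and 5 | Apply to other tumor groups |
| Sponsor approval | Required for other INI1-negative tumors in Cohort 3; not required here |
| 4.3 exclusions | None concerns INI1 or SMARCA4 status |
| 8.5.8.1 | Central testing is planned but is not a condition of entry |

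None of these closes it. The word that narrows the category (selected) is not defined.

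**Step 2: reproduce the stated design.** Inputs from Section 14.2.1 are n = 20, success if at least 3 respond, null ORR 5% and ORR of interest 20%. With X ~ Binomial(20, p), P(X ≥ 3) = 1 − P(0) − P(1) − P(2).

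- p = 0.05: 1 − (0.3585 + 0.3774 + 0.1887) = 0.0755. The plan states a Type I error of 8%.
- p = 0.20: 1 − (0.0115 + 0.0576 + 0.1369) = 0.794, so the Type II error is 0.206. The plan states 21%.

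Both figures reproduce.

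**Step 3: let k of the 20 subjects lack the loss.** The documents give neither k nor the response rate q of such subjects. Both are assumptions: k = 2, 3 or 5, and q = 0% or 5%. Subjects with loss respond at 20%. Then X = A + B, with A ~ Binomial(20 − k, 0.20) and B ~ Binomial(k, q), and the expected ORR is [0.20(20 − k) + qk]/20.

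Worked case, k = 5. For A ~ Binomial(15, 0.20), P(0), P(1) and P(2) are 0.0352, 0.1319 and 0.2309.

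- q = 0%: 1 − (0.0352 + 0.1319 + 0.2309) = 0.602.
- q = 5%: for B ~ Binomial(5, 0.05) the same three terms are 0.7738, 0.2036 and 0.0214. Convolving gives P(X = 0) = 0.0272, P(X = 1) = 0.1092 and P(X = 2) = 0.2063. So P(X ≥ 3) = 1 − 0.3427 = 0.657.

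| k of 20 | Expected ORR, q = 0% | P(≥3), q = 0% | Expected ORR, q = 5% | P(≥3), q = 5% |
|---|---|---|---|---|
| 0 | 20.0% | 79.4% | 20.0% | 79.4% |
| 2 | 18.0% | 72.9% | 18.5% | 74.6% |
| 3 | 17.0% | 69.0% | 17.75% | 71.8% |
| 5 | 15.0% | 60.2% | 16.25% | 65.7% |

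**Step 4: Type I error.** Now set the subjects with loss at the null rate of 5%. If q = 5%, all 20 respond at 5% and the error stays at 0.0755 for every k. If q = 0%, it falls: 0.058 at k = 2, 0.050 at k = 3 and 0.036 at k = 5.

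**The case against.** The strongest reply is that this is a drafting slip with no shown consequence. Several parts of that reply stand.

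- **No such enrollment is documented.** A reader might infer that the Cohort 2 ORR has in fact been diluted. The documents do not support that: they give no count of rhabdoid-features tumors in Cohort 2 and none without the loss. Table 1 in Section 1.4.2 even lists that tumor type within a combined INI1 group. This is weak reassurance, because the same group includes synovial sarcoma and may include escalation subjects.
- **The Cohort 2 objective is worded by histology.** Section 2 refers to non-ATRT rhabdoid tumors. Section 3.1 is a design summary and cannot be an exhaustive molecular definition, since the study also took synovial sarcoma, where Section 1.1 describes INI1 deficiency without mutation or deletion of the gene. The ORR for the objective as worded is therefore not biased by definition; the difficulty is one of interpretation.
- **Sites have other cues.** The study description names the target, Section 15.5 sends eligibility questions to the Medical Monitor, and central testing could reveal a case after entry. None of these is an entry requirement, so the gap remains.
- **Central results may be incomplete.** Section 8.5.8.1 plans testing as appropriate, and part of its text is redacted. A result for every Cohort 2 subject cannot be assumed.

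The reply does not remove the mismatch between Sections 4.2.1 and 4.2.2. Section 3.3 explains how the expansion cohorts were formed and gives no reason for a narrower biomarker rule.

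**Conclusion.** The two criteria conflict, and the expansion wording should be corrected. This is an internal inconsistency rather than a design choice, and it ranks as something that should be fixed. Certainty is high for the mismatch itself and lower for its effect, which depends on a subgroup of unknown size that may be empty.

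Under the assumptions in the working, the loss of power is about 5 to 6.5 percentage points with 2 of 20 subjects without the loss, and about 14 to 19 points with 5 of 20. The risk is a missed signal in one cohort. A reader might also infer that the false-positive rate or the sample size is wrong; neither follows. The stated error rates reproduce, and Type I error does not rise if subjects without the loss respond at 5% or less.

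**What to change.** Reconcile Section 4.2.2, criterion 3, and the synopsis with the scope in Section 4.2.1: "For subjects with ATRT, MRT, RTK, or tumors with rhabdoid features only". If all Cohort 2 subjects then have the loss, the design keeps its stated properties. The sample size and the 3-of-20 rule do not change.

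If any Cohort 2 subject was enrolled without documented loss, add to the SAP a supportive Cohort 2 ORR restricted to subjects with documented INI1 or SMARCA4 loss. Use local or central results where available and report how many subjects have neither. The all-treated ORR stays primary.

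The cost is a short amendment in the protocol's own wording and, if needed, one extra table. Tissue is already required at entry. The downside is that an occasional subject without documented loss becomes ineligible.

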4.3 Exclusion Criteria

Subjects meeting ANY of the following criteria must NOT be enrolled in this study:

1. Has had prior exposure to tazemetostat or other inhibitor(s) of EZH2.
2. Is being actively treated for another concurrent malignancy or is less than 5 years from completion of treatment for another malignancy.
3. Has participated in another interventional clinical study and received investigational drug within 30 days or five half-lives, whichever is longer, prior to the planned first dose of tazemetostat.
4. Has had major surgery within 2 weeks prior to enrollment.
NOTE: Minor surgery (e.g., minor biopsy of extracranial site, central venous catheter placement, shunt revision) is permitted within 2 weeks prior to enrollment.
5. Has thrombocytopenia, neutropenia, or anemia of Grade ≥ 3 (per CTCAE 4.03 criteria) or any prior history of myeloid malignancies, including myelodysplastic syndrome (MDS). Has abnormalities known to be associated with MDS (e.g. del 5q, chr 7 abn) and MPN (e.g. JAK2 V617F) observed in cytogenetic testing and DNA sequencing.
NOTE: Bone marrow aspirate/biopsy will be conducted following abnormal peripheral blood smear morphology assessment at Screening. Cytogenetic testing and DNA sequencing will be conducted by a central laboratory following an abnormal result of bone marrow aspirate/biopsy.
6. Has a prior history of CCI/T-ALL.
7. Has clinically active heart disease including prolonged QTcF (>450 msec).
8. Is currently taking any prohibited medication(s) as described in Section 7.3.

9. Is unwilling to exclude grapefruit juice, Seville oranges and grapefruit from the diet and all foods that contain those fruits from time of enrollment to while on study.
10. Has an active infection requiring systemic treatment.
11. Is immunocompromised (ie, congenital immunodeficiency), including subjects with a known history of infection with human immunodeficiency virus (HIV).
12. Has known history of chronic infection with hepatitis B virus (hepatitis B surface antigen positive) or hepatitis C virus (detectable HCV RNA).
13. Has had a symptomatic venous thrombosis within 14 days prior to study enrollment.
NOTE: Subjects with a history of a deep vein thrombosis 14 days prior to study enrollment who are on anticoagulation therapy with low molecular weight heparin are eligible for this study.
14. **For subjects with CNS involvement (primary tumor or metastatic disease):** Have any active bleeding, or new intratumoral hemorrhage of more than punctate size on Screening MRI obtained within 14 days of starting study drug, or known bleeding diathesis or treatment with anti-platelet or anti-thrombotic agents.
15. Has known hypersensitivity to any of the components of tazemetostat or other inhibitor(s) of EZH2, or hypersensitivity to Ora-sweet or methylparaben.
16. Has an uncontrolled intercurrent illness including, but not limited to, uncontrolled infection, or psychiatric illness/social situations that would limit compliance with study requirements.
17. **For female subjects of childbearing potential:** Is pregnant or nursing
For male subjects: Is unwilling to adhere to contraception criteria from time of enrollment in study to at least 3 months after last dose of tazemetostat.

5 INVESTIGATIONAL PRODUCT

5.1 Description

Tazemetostat (EPZ-6438) is an Epizyme investigational product (IP) and is defined as an Investigational Medicinal Product (IMP) under the European Union Clinical Trials Directive (EU CT Dir). Two formulations will be used in this trial: oral suspension and tablets.

The contents of the package label will be in accordance with all applicable regulatory requirements. The expiry date will be printed on the label.

Oral Suspension

	Investigational Product
Product name:	Tazemetostat (EPZ-6438)
Formulation description:	Oral Suspension of Tazemetostat API suspended in an Ora-sweet mixture
Dosage form:	Powder for Oral Suspension
Physical Description:	A powder for oral suspension in HDPE bottles or foil-laminate pouches.
Route/Schedule/Duration:	Oral/ BID/Continuous

Abbreviations: BID, twice daily; HDPE, high-density polyethylene

Tablet Formulation (Cohort 4 Only)

	Investigational Product
Product name:	Tazemetostat (EPZ-6438)
Formulation description:	200 mg tablet
Dosage form:	Tablet
Physical description:	Red, round, and biconvex film-coated tablets packaged in white high-density polyethylene bottle with a child resistant, tamper-evident polypropylene screw cap
Route/Schedule/Duration:	Oral/TID/Continuous

Abbreviations: TID, three times daily

5.2 Preparation, Handling, and Storage of IP

Preparation: The oral suspension is prepared by mixing the tazemetostat powder with Ora-sweet® to produce an oral suspension of 30 mg tazemetostat (as free base) per mL of suspension. Please see Pharmacy Manual for details. No preparation is required for the tablet formulation.

Handling: Please see Pharmacy Manual for details.

Storage: Please see Pharmacy Manual for details.

5.3 Dosage and Administration

Tazemetostat must be dispensed or administered only to subjects enrolled in the study and in accordance with the protocol. Standard institutional procedures for administering an oral agent via by mouth will be followed. An adequate supply will be provided with instructions on home administration.

Tazemetostat administered to newly enrolled subjects: Based on benefit-risk assessment of the population studied in this clinical trial, following a report of CCI in a pediatric patient, from the time Amendment 7.0 approval to the completion of enrollment, the following doses will be the starting dose for new enrolled patients: For new patients with ATRT or any INI1-negative tumors with CNS involvement, the starting dose will remain 1200 mg/m² BID. For new patients that are non-ATRT, the starting dose will be 520 mg/m² BID. (See Section 6.5.3).

Tazemetostat administered as an oral suspension: The starting dose of tazemetostat (for dose escalation only) will be 240 mg/m²/dose given BID (based on free base) = 480 mg/m²/day. The amount of suspension per dose is calculated based on the subject's body surface area (BSA) and the assigned dose level. After the completion of Cycle 1, if a subject is unable to continue dosing with the oral suspension formulation due to adherence issues, the Medical Monitor should be contacted to discuss the possibility of switching to tablet dosing options.

Tazemetostat administered as a tablet (subjects in Cohort 4 only; Cohort 4 is closed to enrollment): Tazemetostat will be orally administered at the dose of 800 mg/m² TID (2400 mg/m²/day). Please see CCI for tablet dosing nomogram. This will provide instruction on the number of tablets to be taken based on BSA. After the completion of Cycle 1, if a subject is unable to continue dosing TID with the tablet formulation because of the quantity of tablets or schedule, the Medical Monitor should be contacted to discuss the possibility of switching to BID tablet dosing or BID suspension dosing.

For subjects on the tazemetostat BID oral suspension schedule, doses should be administered as close to 12 hours apart as possible, but there should be no less than 8 hours between doses. For subjects on the TID tablet schedule, doses should be administered as close to 8 hours apart as possible, but there should be no less than 4 hours between doses. Doses may be taken with or without food.

Vomiting: If the subject vomits within 30 minutes of dosing, anti-emetics should be given and a second dose of tazemetostat given. All doses given, missed and vomited, should be recorded.

Refer to the Pharmacy Manual for more information on drug suspension calculation, preparation, and handling.

Missed Doses

Tazemetostat doses must be taken at least 8 hours apart for BID dosing and at least 4 hours apart for TID dosing. If a dose is missed (e.g., missed morning dose or vomited and did not re-dose within appropriate time) it should not be taken if it is less than 8 hours until the next dose for BID dosing or less than 4 hours until the next TID dosing.

